6.0 SAMPLING METHOD

Rheumatoid Arthritis patients will be sampled from the Medical Clinic, Hospital Universiti Sains Malaysia. Convenient sampling, under the niche of non-probability sampling method, will be adopted in the study. Accessible population are registered medium to severe stage RA patients. The study will take place at the Clinical Trial Ward of HUSM in Kubang Kerian, Kelantan, Malaysia from 30th May 2019 to March 2020.

7.0 INCLUSION AND EXCLUSION CRITERIA

a. Inclusion criteria

Inclusion criteria for the clinical trial are:

- RA patients according to the American College of Rheumatology (ACR)

- Moderate (DAS 28 = 3.2 – 5.1) and severe (DAS 28 > 5.1) RA manifestation
- Chronological age: 21 years and above
- Stable RA patients who are receiving NSAIDs, glucocorticoids/DMARDs (for example leflunomide, methotrexate, sulfasalazine and hydroxychloroquine) for at least 3 months prior to entering the study
- Not taking antioxidant/antiinflammatory supplements

(Example of antioxidant: vitamin C, vitamin E, grape seed extract, garlic capsule, ginkgo biloba)

(Example of anti-inflammatory supplement: fish oil, curcumin extract, ginger extract, spirulina)

b. Exclusion criteria

Exclusion criteria for the clinical trial are:

- Having liver (chronic liver failure, cirrhosis, all types of hepatitis), kidney (chronic kidney disease, haemodialysis) or haematological (anaemia, thalassemia, haemophilia) disorders
- Active gastric/duodenal ulcer
- Psychiatric disease/mental retardation (bipolar disorder, depression, schizophrenia)
- Cancer (all types), Diabetes Mellitus (Type I and II), uncontrolled hypertension (BP at 140/90 mmHg for the past 3 months), and endocrine disorders (Cushing's disease, gigantism and hyperthyroidism).
- Alcohol and drug abuse (self-mentioned or as recorded in the medical card)
- Other autoimmune/inflammatory diseases (systemic lupus erythematosus, multiple sclerosis, gout, psoriasis, chronic inflammatory demyelinating polyneuropathy)
- Pregnancy/lactation
- Hormone replacement therapy (for at least 3 months prior to entering the study)
- Herbal remedies (any parts from the plants such as flowers, rhizome, seeds, roots, leaves, fruits, stems)
- Vegetarian patient (pure vegan)
- Gluten intolerance
- Participations from another supplementary program

8.0 VULNERABILITY OF THE SUBJECT/PARTICIPANT

The principle investigator and co-investigators will comply with the applicable regulatory requirement(s) related to the reporting of unexpected serious adverse drug reactions to the

regulatory authorities and the institutional review board. Any complaints (particularly gastrointestinal discomfort) from the subject will be recorded, and they will be arranged to receive immediate medical care at HUSM. If the complaints persist during supplementation period, the subject will be stopped by the investigator from the trial. The affected subject will be followed up tightly.

9.0 RECRUITMENT OF SUBJECT/PARTICIPANT & INFORMED CONSENT SEEKING

All RA patients will be invited face-to-face during their routine medical follow-up in the medical clinic. Advertisement poster and flyer will be placed in the clinic to attract participation. Research information will be provided to the patients. If they are eligible, informed consent will be obtained. In obtaining and documenting informed consent, the research team will comply with the applicable regulatory requirement(s), and adhere to GCP and to the ethical principles that have their origin in the Declaration of Helsinki. The research team will not coerce or unduly influence a subject to participate in the trial.

10.0 ASSENT FORM REQUIREMENT

Not applicable

11.0 RANDOMIZATION, MATCHING AND BLINDING

(a) Randomization

Step 1: Generation of an unpredictable allocation sequence

To generate a random allocation sequence, a computer-generated list of random numbers will be used. Simple randomization, where a 1:1 allocation ratio (1 supplement group: 1 control group) will be applied.

Step 2: Concealment of this sequence from the investigators enrolling participants

The allocation sequence will be concealed from the investigator enrolling and assessing participants in sequentially numbered, opaque, sealed and stapled envelopes. To prevent subversion of the allocation sequence, the name and date of birth of the participant will be written on the envelope.

Step 3: Implementation

Determination of whether a patient would be supplemented by multigrain powder (S) or control (C) will be made by reference to a statistical series based on random sampling numbers drawn up by statistician; the details of the series are unknown to any of the investigators or to the coordinator. After acceptance of a patient by the panel, the appropriate numbered envelope will be opened at the clinical trial ward; the number indications inside will be notified if the patient will be S or a C group, and this information will be then given to the medical officer in charge of the trial.

(b) Matching

Not applicable.

(c) Blinding

Participants will be notified whether they have been randomly assigned into either the S or C group since this is an open-labelled trial. However, only data collectors, coordinator and medical officer in charge of the trial are aware of the allocated arm. Investigators, data analyst and outcome adjudicator will be kept blinded to the allocation.

12.0 SUITABILITY OF STUDY AREA/STUDY LOCATION

The established Clinical Trial Unit, located in the HUSM will be used to conduct the clinical trial. The mentioned clinical trial unit is the referred clinical trial hub in southern region of Malaysia. The clinical trial unit is equipped with 3 beds for patients' observation, medication supply room, seminar room, prayer room, centrifugation room, case report files room, diagnostic lab and restroom. All staffs in the clinical trial unit is good clinical practice (GCP) certified.

13.0 VALIDITY OF RESEARCH INSTRUMENTS

Key indicators of the quality of a measuring instrument are the reliability and validity of the measures. Validity is the extent to which the interpretations of the results of a test are warranted, which depends on the particular use the test is intended to serve. In this study, the validity of the research instruments will be measured via self-report and secondary data sources. Validity evidence from established instruments is maintained when the instrument is used in the same

form and follow the same administration procedures. Overall, the validity of the research instruments will be assessed as below:

- Calibrated and reliable research instruments (refer methodology)
- Hypothetical or abstract concepts (constructs), such as severity of disease, supplement efficacy, supplement safety, burden of illness, patient satisfaction, quality of life, quality of provider–patient communication, and adherence to supplement regimens, will be measured

To generate a random allocation sequence, a computer-generated list of random numbers will be used. Simple randomization, where a 1:1 allocation ratio (1 supplement group: 1 control group) will be applied.

Step 2: Concealment of this sequence from the investigators enrolling participants

The allocation sequence will be concealed from the investigator enrolling and assessing participants in sequentially numbered, opaque, sealed and stapled envelopes. To prevent subversion of the allocation sequence, the name and date of birth of the participant will be written on the envelope.

Step 3: Implementation

Determination of whether a patient would be supplemented by multigrain powder (S) or control (C) will be made by reference to a statistical series based on random sampling numbers drawn up by statistician; the details of the series are unknown to any of the investigators or to the coordinator. After acceptance of a patient by the panel, the appropriate numbered envelope will

be opened at the clinical trial ward; the number indications inside will be notified if the patient will to be S or a C group, and this information will be then given to the medical officer in charge of the trial.

(ii) Matching

Not applicable.

(iii) Blinding

Participants will be notified whether they have been randomly assigned into either the S or C group since this is an open-labelled trial. However, only data collectors, coordinator and medical officer in charge of the trial are aware of the allocated arm. Investigators, data analyst and outcome adjudicator will be kept blinded to the allocation.

(c) Study Outcomes

The patient outcome measures will be assessed at two time points: baseline and end of treatment period (week-12).

(i) Primary clinical outcomes

The primary efficacy criterion is clinical remission as assessed by changes in the DAS-28 score from baseline (Day 0) to end of treatment (week-12).

1. Disease Severity Score (DAS-28)

Assessment of number of tender (t28) and swollen (s28) joints out of 28 (10 proximal interphalangeal, 10 metacarpophalangeal, 2 wrists, 2 elbows, 2 shoulders and 2 knees) will be conducted by a rheumatologist and the validated DAS-28 form will be filled to calculate disease activity index according to the following formula:

$$\text{DAS-28} = 0.56 \sqrt{t28} + 0.28 \sqrt{s28} + 0.70 \ln(\text{ESR}) + 0.014 \text{ VAS} \quad (\text{Harrison et al., 2008})$$

Where ESR = erythrocyte sedimentation rate

 VAS = Visual Analogue Scale

DAS-28 is recommended by the European League Against Rheumatism (EULAR) as the only gold standard to measure the disease activity in patients with RA (Pincus, 2005).

2. Health Assessment Questionnaire-Disability Index (HAQ-DI)

The Health assessment questionnaire disability index (HAQ-DI) is a questionnaire for the assessment of RA. The questionnaire is a patient reported outcome (PRO) which is usually self-administered by the patient.

The following categories will be assessed by using the HAQ-DI:

- dressing and grooming
- arising
- eating
- walking
- hygiene
- reach
- grip
- common daily activities

The patients report the amount of difficulty they have in performing some of these activities. Each question asks on a scale ranging from 0 to 3 if the categories can be performed without any difficulty (scale 0) up to cannot be done at all (scale 3). HAQ has been conducted by the Stanford Arthritis, Rheumatism, and Aging Medical Information System (ARAMIS) more than 200,000 times in routine and research contexts, and is also recommended by the ACR to measure physical functionality. Test-retest correlations confirming reproducibility were ranged from 0.87 to 0.99, and correlations between interview and questionnaire formats were ranged from 0.85 to 0.95 (Bruce & Fries, 2003)

3. Visual Analogue Scale (pain severity)

The patients will evaluate their own pain severity on a 100 mm VAS (from 0 mm = no pain to 100 mm = extreme pain) with 5 mm intervals. The standard VAS is a 10 cm scale with a border on each side. To the left of the “0” mark appears the indication “No pain at all”, and to the right of the “10” mark “Pain as bad as it could be”. The visual analog pain scale has proven a great advance in the assessment of pain.

(ii) Secondary outcomes

Twelve-hour fasting blood samples will be collected by venipuncture at baseline and week-12. 20 ml blood samples will be taken according to a standard protocol and immediately centrifuged. Then, the samples will be stored at -80°C until further analysis at the USM reference laboratory.

- General health outcomes

- Full blood count
- Lipid profile
- Erythrocyte Sedimentation Rate (ESR)
- Liver function test
- Kidney function test
- C-reactive protein (CRP)

- Serum inflammatory molecules

Serum inflammatory molecules (IL-6, IL-1 β and tumor necrosis factor- α), histidine-C-reactive protein (hs-CRP), and matrix metalloproteinase-3 (MMP-3) will be determined by human high sensitivity ELISA kits.

The only blood tests that are routinely used to assess disease activity in RA are the ESR and CRP (Peabody et al., 2013). Study found that IL-6 plays a key role in the development of RA disease (Yoshida & Tanaka, 2014). A transient synthesis of IL-6 contributes to host defense against infectious agents and tissue injuries by inducing acute phase reactions and immunological and hematopoietic responses. Patients with RA have excessive amounts of IL-1. IL-1 including IL-1 β produce the biological effects attributed to this cytokine (Kay & Calabrese, 2004). Tumor necrosis factor- α (TNF- α) as a key molecule in the control of inflammatory production. Individuals with RA have high levels of TNF- α in the synovial fluid and it plays an important role in inflammation and joint destruction that are hallmarks of RA (Vasantha et al., 2007). Histidine-C-reactive protein (hs-CRP) was detected before the onset of RA and also indicated the activity of the disease during the course of the disease (Nielen et al., 2004). Study showed elevated MMP-3 serum levels reflect disease activity in RA patients and can be used as a specific marker for joint damage (Fadda et al., 2016)

(iii) Tertiary outcomes

- Nutritional status (body weight, standing height, BMI changes, body composition, dietary habits)
 - Weight and height (SECA, Hamburg, Germany) will be determined at the beginning and the end of the study in a fasting status without shoes and minimal clothing by a trained nutritionist. BMI will be calculated using the height and weight measurements. Body composition (fat mass, fat free mass, total body water) will be measured using TANITA InnerScan.
 - Nutrients intakes will be estimated using dietary history questionnaire (DHQ) at baseline and at the end of the trial for 3 days. The subjects will be reminded not to change their usual diets and physical activities throughout the study, and any changes in their medications will be avoided if possible.
- Peripheral antioxidant status and oxidative stress [Total antioxidant capacity (TAC), antioxidant capacity; malondialdehyde (MDA) concentration lipid oxidation; protein carbonyl, protein oxidation; superoxide dismutase (SOD), enzymatic activity; hydrogen peroxide, free radical; and Comet assay, DNA damage] will be measured using commercial kits.

Comet assay is an adaptable and potential tool for estimating the extent of DNA damage and repair efficacy in various clinical conditions including rheumatoid arthritis as this disease prone to free radical damage and decreased efficacy of DNA repair mechanism (Gunasekarana et al., 2015)

(d) Compliance to the study protocol

Compliance with the supplement intake will be assessed by counting number of the sachets used at every follow up visit. For control group, standard medication will be remained unchanged, if possible.

(e) Promotion of the Trial Adherence

Trial adherences will be promoted via continuous encouragement and tight follow up with the respected patients through face-to-face dialogue and phone conversation. The study will apply maximum adherence by using intact interviewer for each subject. Continuous financial remuneration and refreshment will be given to subject at each appointment and follow up sessions. Reimbursement of transportation mileage and remuneration will be provided to each subject.

15.0 CONTROL GROUP

Control group will be the existing medium to severe-stage RA patients, who are currently receiving his/her standard or preceding medical treatment/regimen. They will be reminded not to alter their habitual dietary intake during the clinical trial period.

16.0 POTENTIAL RISK TO SUBJECT/PARTICIPANT

16.1 Known potential risks

- (a) The new intervention may not work, or it may not be better than the standard treatment.
- (b) Patients may expose to side effects, mainly abdominal discomfort for supplements.
- (c) Patients will be randomly assigned into either supplement (active) or standard care (control) group.
- (d) Patients will be requested to undergo more frequent testing (for blood withdraw specifically) and doctor visit.

16.2 Known potential benefits

- (a) Assess to complementary medicine that isn't tested yet. This complementary medicine may be more effective or alleviate side effects than the treatments that are currently available.
- (b) Patient will play a more active role in their own health care. This can lead to a more positive outlook and better quality of life.
- (c) Regular and careful attention will be provided to the subject. Researchers may provide the patient with medical care and more frequent health check-ups as part of their treatment.
- (d) Patients are given opportunity to contribute to research that may help others get a better treatment for their health problems in the future.

17.0 DIRECT & INDIRECT BENEFIT TO SUBJECT/PARTICIPANT

17.1 Direct benefit

- (a) Patients will be given opportunity to have better access to health care
- (b) The trial is expected capable to increase the quality of life of patients.
- (c) Patients are expected to have knowledge gain about their health problem.

17.2 Indirect benefit

- (a) Patients will be motivated to feel diversion from routine, the opportunity to meet with other people and to feel useful and helpful.
- (b) All patients will be paid in the form of reimbursement/remuneration.

18.0 DATA/SPECIMEN HANDLING

(a) Data handling

The planned clinical trial data management activities are:

- Data acquisition/collection
 - Data collection is the responsibility of the clinical trial staff at the site under the supervision of the PI. The investigator is responsible for ensuring the accuracy, completeness, legibility, and timeliness of the data reported.
 - The use of case report form (CRF) as data reporting document will allow efficient and complete data collection, processing, analysis and reporting. Paper CRF, together with electronic CRF (eCRF) will be applied, together with an instruction manual. One CRF book will be prepared for each subject enrolled in the study. All investigator will ensure the accuracy, completeness, legibility, and timeliness of the data reported on the CRFs and in all required reports. Only data outlined in the trial protocol will be collected. Only designated members of the research staff should be allowed to record and/or correct data in the CRFs.
- Data abstraction/extraction
 - Data will be taken from the source documents (e.g.: medical record) and entered onto the CRFs by study personnel. Clinical data (including AEs, concomitant medications, and expected adverse reactions data) and clinical laboratory data will be entered into the data capture system. The data system includes password protection and internal quality checks.
- Data entry, data processing/coding

- Data entry may take a form of direct computer entry by a person transferring data from paper-based CRFs into a computer database. Data entry allows the process of entering information into a computer for further processing. Coding may be used to represent data category.
- Data storage
 - No records will be destroyed without the written consent of the sponsor, if applicable. It is the responsibility of the sponsor to inform the investigator when these documents no longer need to be retained. Study documents should be retained for 7 years after the completion of the trial.
- Data quality control and assurance
 - Quality control will be applied to each stage of data handling to ensure that all data are reliable and have been processed correctly. Ongoing and concurrent review of subject data will be conducted, in conjunction with the verification of all data collected and abstracted.
 - Quality assurance will be implemented via planned and systematic check. Verification is compulsory to make sure that the trial is performed as per the plan. Checking will be conducted to ensure that staff is compliant with internal and external regulations/guidelines.

(b) Blood collection and storage

One registered medical officer and one staff nurse will be assigned to take 20 ml blood from all patients. Lithium heparinized blood tube, EDTA blood tube and serum separating tube (SST) will be used. On-site processing of serum and plasma will be carried out at centrifugation room. Storage temperature will be set at -80⁰C. Aliquot freezing will be applied. Samples will be frozen once, and thawed once by the researcher.

19.0 DURATION OF PARTICIPANT INVOLVEMENT

The subjects will be involved in the trial for up to a 12 weeks period.

20.0 WITHDRAWAL CRITERIA

The investigator may terminate participation in the study if:

- (a) The participant will be terminated if they meet an exclusion criterion (either newly developed or not previously recognized) that precludes further study participation.
- (b) Any clinical adverse event (AE), serious adverse events (SAEs), laboratory abnormality, or other medical condition or situation occurs such that continued participation in the study would not be in the best interest of the participant.
- (c) The participant will be terminated if they take any probiotic during the study time. However, the use of antibiotic is allowed if it is needed.

All withdrawals and dropouts of enrolled subjects from the trial will be reported and explained on the CRFs. Any terminated/withdrawal will be follow up if possible.

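### Intention-to-treat is promised, but no week-12 DAS-28 is named for patients taken out of the trial early, so the primary comparison can become a completers analysis

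*Combined protocol and SAP*

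**What the plan says.** Section 21.0 states that the analysis will be by intention-to-treat. It defines no analysis set and gives no rule for randomised patients without a week-12 value. It lists several methods for all outcomes together, including mixed models and analysis of covariance, and assigns none to the primary endpoint.

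Two other sections remove patients after randomisation:

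- Section 8.0, on complaints, particularly gastrointestinal ones: "If the complaints persist during supplementation period, the subject will be stopped by the investigator from the trial". The next sentence is "The affected subject will be followed up tightly".
- Section 20.0(a): "The participant will be terminated if they meet an exclusion criterion (either newly developed or not previously recognized) that precludes further study participation".
- Section 20.0(b): adverse events, laboratory abnormalities or other conditions such that "continued participation in the study would not be in the best interest of the participant".
- Section 20.0(c): "The participant will be terminated if they take any probiotic during the study time".

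Section 20.0 closes with "All withdrawals and dropouts of enrolled subjects from the trial will be reported and explained on the CRFs" and "Any terminated/withdrawal will be follow up if possible".

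Section 14.0(c) places the outcome measures at baseline and week 12 only. The primary criterion is the change in DAS-28 between those two points. Section 5.0 plans 21 per arm, allows for 20% dropout and arrives at 25.

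**The concern.** An intention-to-treat comparison needs the outcome of everyone randomised, including those who stopped. Here a patient removed before week 12 and not brought back has no post-baseline primary value at all. If that happens, the DAS-28 comparison rests on those who stayed. It is biased if the patients who leave differ in outcome from those who remain and if this selection differs between arms.

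The documents give one reason to expect such a difference. Section 16.1 names abdominal discomfort as the main side effect of the supplement, and section 8.0 removes patients whose complaints persist. The plan expects dropout, so missing primary values are foreseen, but it does not say how they will be handled.

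**Working it through.** **Can a removed patient lack the primary outcome under the stated rules?** Yes. Sections 8.0 and 20.0 end trial participation, not only supplementation. Section 14.0(c) has no DAS-28 between baseline and week 12. Neither follow-up sentence names a visit, a time point or a DAS-28. The statement in section 14.0(a) that baseline procedures are repeated after week 12 is the general schedule and does not say that it covers patients whose participation has ended.

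**Do the listed methods repair this?** No. Analysis of covariance and regression would normally drop a patient without a week-12 value. A mixed model keeps the baseline value, but with one post-baseline time point such a patient adds almost nothing to the treatment contrast. That contrast still rests on completers, under a missing-at-random assumption that the plan does not state.

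**The plan's sample size.** Section 5.0 gives z values of 1.96 and 0.8416 and n = 21, but no value for the standardised effect, so n cannot be reproduced forward. Solving backward: √(2 × (1.96 + 0.8416)² / 21) = 0.865 SD. The step 21 + 4 = 25 leaves room for 4/25 = 16% loss. The stated 20% of 25 is 5 patients. Both are shown below.

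**Illustrative bias.** The documents give no removal rate by arm or cause. Assumptions: no true effect, loss in the supplement arm only, unadjusted two-sided 5% t-test (noncentral t), SD of 1. The gap is how much worse the removed patients would have scored than completers. Bias = fraction removed × gap.

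| Removed | Gap 0 | Gap 0.25 SD | Gap 0.5 SD | Gap 1.0 SD |
|---|---|---|---|---|
| 2 of 25 (8%) | 0; 5.0% | 0.02 SD; 5.1% | 0.04 SD; 5.2% | 0.08 SD; 5.8% |
| 4 of 25 (16%) | 0; 5.0% | 0.04 SD; 5.2% | 0.08 SD; 5.8% | 0.16 SD; 8.3% |
| 5 of 25 (20%) | 0; 5.0% | 0.05 SD; 5.3% | 0.10 SD; 6.2% | 0.20 SD; 10.0% |

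Each cell gives the bias and then the false-positive rate. Equal loss with equal gaps in both arms cancels: 0.16 − 0.16 = 0. Loss in controls only reverses the sign.

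**Baseline adjustment.** Adjusted bias = fraction × gap − slope × fraction × baseline gap. With 16% removed, a gap of 1.0 SD and an assumed slope of 0.5:

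- baseline gap 0: 0.16 − 0 = 0.16 SD
- baseline gap 0.5 SD: 0.16 − 0.5 × 0.16 × 0.5 = 0.12 SD
- baseline gap 1.0 SD: 0.16 − 0.5 × 0.16 × 1.0 = 0.08 SD

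Adjustment removes only the part of the gap that baseline explains.

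**Power if everyone is followed.** Assume that a fraction f of the supplement arm stops and gains nothing. The effect is (1 − f) × 0.865 SD. The supplement arm is then a mixture with variance 1 + f(1 − f) × 0.865², which is averaged with the control variance of 1. With 25 per arm:

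| f | Effect | Supplement-arm variance | Effect / pooled SD | Power |
|---|---|---|---|---|
| 8% | 0.795 | 1.055 | 0.785 | 78% |
| 16% | 0.726 | 1.100 | 0.709 | 69% |
| 20% | 0.692 | 1.120 | 0.672 | 64% |

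By the same t-test, 21 evaluable per arm with no dilution gives 78%.

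**The case against.** The strongest counter-argument is that the one group for which the documents suggest unequal loss, patients with persistent complaints, also has the firmest follow-up wording. Section 8.0 promises it without condition. That stands, and it lowers the likely loss in that group. But the sentence follows directly on text about medical care and names no efficacy assessment. It also does not reach removals for probiotic use or exclusion criteria. For those routes the documents give no specific reason to expect a difference between arms.

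A reader might infer that removal ends outcome collection, so that sections 8 and 20 flatly contradict section 21. The documents do not say so. Both sections provide some follow-up, and read together with section 21 they can mean continued follow-up where feasible. The consent pages are not in the copy reviewed, so any terms there cannot be checked. What stands is that the text permits the loss and does not secure the value.

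The removal routes are also limited: 20(a) requires a criterion that precludes participation, and 20(b) turns on the patient's interest. Contact by dialogue and phone (section 14.0(e)) and the CRF record of withdrawals make loss rarer and visible, but they do not supply a DAS-28.

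Finally, most of the illustrated figures are small. For gaps up to 0.5 SD the bias is at most 0.10 SD against a back-solved effect of 0.865 SD. That is fair, and it limits the weight of the point.

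**Conclusion.** The point holds as a risk that the text permits. The plan promises an analysis of everyone randomised, removes some patients after randomisation, and nowhere secures or substitutes their week-12 DAS-28. Following the stated rules can therefore yield a completers comparison.

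A reader might go further and conclude that the result will be biased in favour of the supplement. The documents do not support that: they give no removal rates by arm and nothing on how removed patients would have scored. In the one-arm illustration the false-positive rate runs from 5.0% to 10.0%, and it passes 6.2% only when removed patients are assumed to be a full SD worse. Nor should unequal loss be inferred from the visit schedule. Section 14.0 lists different attendances by arm, but it also speaks of monthly review of patients, as does section 22.0.

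The sponsor should make the change, because it is cheap. Confidence is medium: the gap in the text is clear, and its consequence is uncertain.

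**What to change.** Reconcile sections 8.0, 20.0 and 21.0 so that, whatever clinical stopping rule the sponsor uses, stopping the supplement or meeting a section 20 event does not by itself end outcome collection. Specifically:

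1. Name the week-12 DAS-28 in both follow-up sentences.
2. Seek it from every randomised patient unless consent is withdrawn or the assessment is not in the patient's interest, and analyse patients as allocated.
3. In section 21.0, state how week-12 values that are still missing will be handled in the primary analysis. Add one simple sensitivity analysis that varies the assumption about them by arm.

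The cost is wording plus a few more attendances at a visit already planned. Some loss would remain through the two exceptions. The estimate would also include patients who stopped, which dilutes it: under the assumption in the working, power is about 78%, 69% or 64% when 8%, 16% or 20% of the supplement arm stop. That diluted effect is the one the promised intention-to-treat analysis estimates.
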